10.6 lı	nterim analysis and criteria for the premature termination of the tria	Error! Bookmark not defined.
10.7 P	articipant population	Error! Bookmark not defined.
10.8 P	rocedure(s) to account for missing or spurious data	22
10.9	Other statistical considerations	Error! Bookmark not defined.
11. DATA	A MANAGEMENT	22
11.1	Data collection tools and source document identification	22
11.2	Data handling and record keeping	23
	ta handling and record keeping will be kept in adherence to Univers isation(s) policies	•
11.3	Access to Data	23
11.4	Archiving	23
12. MON	IITORING, AUDIT & INSPECTION	23
13. ETH	ICAL AND REGULATORY CONSIDERATIONS	23
13.1	Research Ethics Committee (REC) review& reports	23
13.2	Peer review	24
13.3	Public and Patient Involvement	24
13.4	Regulatory Compliance	24
13.5 P	rotocol compliance	24

13.7 Financial and other competing interests for the chief investigator, PIs at each site and comm members for the overall trial management	25
13.8 Indemnity	25
13.9 Post trial care	25
13.8 Access to the final trial dataset	25
14. DISSEMINIATION POLICY	25
15. REFERENCES	25
16. Appendix 1 – Amendment History	26

LIST OF ABBREVIATIONS

Define all unusual or 'technical' terms related to the trial. Maintain alphabetical order for ease of reference.

AE Adverse Event
AR Adverse Reaction
CI Chief Investigator
CRF Case Report Form

CTU Clinical Trials Unit
GCP Good Clinical Practice
ICF Informed Consent Form
ISF Investigator Site File

•

NHS R&D National Health Service Research & Development

PI Principal Investigator

PIC Participant Identification Centre
PIS Participant Information Sheet

QC Quality Control

RCT Randomised Control Trial
REC Research Ethics Committee

SAE Serious Adverse Event

SAR Serious Adverse Reaction

SOP Standard Operating Procedure

TMF Trial Master File

TMG Trial Management Group
TSC Trial Steering Committee

KEY WORDS

Work-related musculoskeletal symptoms (WMS)

State Trait Anxiety Inventory (STAI)

ISSUE Protocol Version v5.0 24/09/2022 IRAS: 300580

TRIAL SUMMARY

Trial Title	Impact of minimally invasive	Impact of minimally invasive surgery on Surgeon Health.				
Trial Participants	Consultant Surgeons and G	Consultant Surgeons and Gynaecologists				
	Patients	Patients				
Planned Sample Size	65 procedures for feasibility	65 procedures for feasibility				
•	100 procedures for validation	on				
Follow up duration	N/A					
Planned Trial Period	2 years					
	Objectives	Outcome Measures				
Primary	variables of the ass (continuous HR monitoring; S Nordic WMS questionna					
Secondary	of 'impact' (high/interme 2. Validation of the combine vs objective assessmen 3. Analysis of the impact of supervision to surgical monitoring 4. Willingness of recruitmes sample size calculations 5. Identification of primare future definitive multi-ce 6. Optimisation/validation measures to capture events and outcomes 7. Safety assessment of recording devices in the 8. Optimisation of surgicular monitoring during programalysis 9. Optimisation of position movement/activity sensionalysis 10. Optimisation/validation of	f providing surgical training and all trainees using heart rate ent of patients/surgeons and so for a future multi-centre study cy/secondary outcomes for a entre study of patient data recording anaesthetic/operative/clinical of measurement tools and a theatre environment				

FUNDING AND SUPPORT IN KIND

FUNDER(S) (Names and contact details of ALL organisations providing funding and/or support in kind for this trial)	FINANCIAL AND NON FINANCIALSUPPORT GIVEN
Intuitive Surgical Grant	Project grant RM60G0742

ROLE OF TRIAL SPONSOR

The sponsor of this research is the University of Leicester. The University of Leicester is registered as a research sponsor with the Department of Health and routinely takes responsibility as sponsor for research activities within the NHS.

ROLES AND RESPONSIBILITIES OF TRIAL MANAGEMENT COMMITEES/GROUPS & INDIVIDUALS

N/A

ISSUE Protocol Version v5.0 24/09/2022 IRAS: 300580

Simulated Setting

series of standardised exercises to ensure partcipants' technical abilities are not impacted by wearing the equipment

PREOP Assessment

PIL and CIL - should have been distributed preoperatively in either a clinic setting or in pre-eassement setting.

PREOP Day of Surgery

On the day consent forms from both consultant and patient to be obtained.

Preop questionnaire to be completed

PARTICIPANT ID TO BE ALLOCATED

INTRAOP

sensors and heart rate monitor will be kept with a member of the research team (CRF [name])

Surgeons will have their own straps to be used at every procedure that they perform that will be included in the study

Sensors and heart rate monitor will be cleaned inbetween cases and participants in line with the established Infection Control standards within the unit where the study is conducted

POST OP

Data downloaded and stored under the specific Participant ID to ensure anonymity and confidentiality. The data will be downloaded onto a phone specifically purchased and setup under a University Research User ID (email) to keep it secure.

Post op questionnaires to be completed

Data trasferred and stored onto the R drive on the Univeristy's secure laptop by Clinical Research Fellow [name]

1. BACKGROUND

The dramatic increase in obesity levels in the UK over the past two decades is having a sustained impact on all types of surgery. The impact on the surgeon of the change from open to MIS has been largely forgotten with the only benchmarking metrics considered being patient or financially focused. Obesity is a major risk factor for work-related musculoskeletal symptoms (WMS) experienced by surgeons, an issue that has the potential to reduce the working life and productivity of surgeons due to high rates of pain, stiffness and fatigue¹. MIS, as compared to open surgery, is associated with significantly greater risk of WMS especially for neck, back, arm/shoulder and leg pain¹. Indeed, WMS have anecdotally increased with 43-100% of surgeons from a wide range of specialties reporting symptoms after performing MIS when questioned. Several factors have been identified as increasing the risk of WMS with straight stick (SS) laparoscopy the most consistently reported being high volume work load and patient obesity². WMS have also been reported to be significantly higher in female surgeons with significantly higher rates of shoulder/neck/upper back discomfort in women with smaller glove sizes compared to men (p=0.004)³.

Impact of surgery on the surgeon is however not confined to musculoskeletal effects but also incorporates human factors issues such as cognitive load and psychological stress⁴. Stress can impair surgical performance⁵, with laparoscopic procedures particularly triggering stress⁶. Measuring surgical stress is very challenging since it requires incorporation of subjective and objective perception of the situation, Thus a self-reported aspect is important when assessing cognitive workload, as is the need for simultaenous real-time assessment⁷. The Imperial Stress Assessment Tool (ISAT) was developed to measure surgeon stress and combines continuous heart rate monitoring with salivary cortisol and an objective questionnaire⁸.

Since its introduction, robotic-assisted surgery (RA) has been reported to have greater benefits for surgeons' musculoskeletal health as compared to SS^{9,10}, although it is not without ergonomics issues typically from fixed position at the console^{11,12}, compared to SS¹³, which instead has a greater impact on shoulder and arm movement¹⁴. RA however does appear to be associated with a lower rate of WMS compared to SS and open surgery when operating on obese patients^{2,15}. RA has also been reported to be less stressful for the surgeon as compared SS¹⁶.

Despite a randomised-controlled trial (RCT) reporting more favourable outcomes for RA as compared to SS ¹⁷ there is the view amongst UK healthcare commissioners that firm evidence supporting a significant advantage for RA over SS in gynaecology is still lacking. Discussions have taken place amongst the GO community in the UK (RCOG/BIARGS/BSGE/NCRI) as well as the general surgical community and currently the consensus is that a RCT of high-BMI EC patients would not be possible due to numerous objections, including lack of equipoise amongst RA surgeons preventing them from randomising patients to SS. A major theme that emerged from these discussions, however, was the high rate of WMS experienced by SS surgeons, since many surgeons report having to take time off for musculoskeletal surgery (shoulder/back) or having to reduce their surgical workload. Consequentially there is great concern as to future service delivery with a reduction in surgeons leading to greater waiting times or even high-BMI patients being denied surgery in favour of less curative non-surgical options, thereby impacting on survival rates.

2. RATIONALE

Minimally invasive surgery (MIS) has a significantly better peri-operative morbidity/mortality compared to open surgery and is the preferred surgical route for the management of numerous conditions. However, the impact of this change on surgeons has been largely forgotten. Obesity is a major risk factor for work-related musculoskeletal symptoms (WMS) experienced by surgeons, an issue that has the potential to reduce the working life and productivity of surgeons due to high rates of pain, stiffness and fatigue. Optimising surgeons' working conditions is vital for their own health and career longevity and also affects patients' safety and outcomes impact on surgical performance.

ISSUE is a feasibility study that aims to develop and validate a multi-faceted assessment tool that can objectively capture the real-time physical and psychological impact performing surgery has on the surgeon. We have previously shown that surgeons require significantly greater muscle movement/activity to complete exercises with standard laparoscopy versus robotic-assisted, and this difference is magnified in case of high BMI patients. The assessment tool will include continuous heart rate monitoring and upper-arm motion sensor monitoring during the procedure; and pre/post procedure WMS and State Trait Anxiety Inventory (STAI) questionnaires. This study has the support of the NCRI EC group and BIARGS.

The outcome of ISSUE will be a validated tool that can be used in a prospective, multi-centre study of open/laparoscopic/robotic surgery, which will provide objective evidence not only of patient outcomes but the impact of the different surgical routes on the surgeon.

3. RESEARCH QUESTION /OBJECTIVES AND OUTCOME MEASURES/ENDPOINTS

Hypothesis: The physical/psychological impact on surgeons is less with RA compared to SS and open surgery.

Aim: To develop and validate a 5-point assessment tool to objectively measure both the physical and psychological impact of complex surgical cases on a surgeon

in order to give a single categorisation of impact: high, intermediate or low.

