3.1 Primary objective

The proportion of surgical procedures where all 4 variables of the assessment tool are captured (continuous HR monitoring; continuous movement sensor monitoring; STAI questionnaire; WMS questionnaire).

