3.2 Secondary objectives

- 1. Analysis to combine the 4 variables to give a single value of 'impact' (high/intermediate/low) per procedure
- 2. Validation of the combined impact values (subjective vs objective assessment)
- To analyse the impact of providing surgical training and supervision to surgical traineeswith varying levels of experience within a live surgical setting using heart rate monitoring as objective measures (if the case has been deemed suitable by the Consultant for the trainee)
- 4. Willingness of recruitment of patients/surgeons and sample size calculations for a future multi-centre study
- 5. Identification of primary/secondary outcomes for a future definitive multi-centre study

- 6. Optimisation/validation of patient data recording measures to capture anaesthetic/operative/clinical events and outcomes
- 7. Safety assessment of measurement tools and recording devices in the theatre environment
- 8. Optimisation of surgeon continuous heart rate monitoring during procedure, data collection and analysis
- 9. Optimisation of positioning and recording of muscle movement/activity sensors and streamlining of data-analysis
- 10. Optimisation/validation of WMS and State Trait Anxiety Inventory (STAI) questionnaires and data analysis
- 11. To include the analysis of the cortisol samples collected at the feasibility stage within the preliminary analysis

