4. TRIAL DESIGN

This is an observational study with the aim of investigating the impact that open and minimally invasive surgery (including robotic assist and straight stick laparoscopy) can have on surgeons' physical and psychological health.

The study will be using a monitoring tracking equipment called XSENS DOT Sensors, Actiheart heart rate monitor which are CE marked and will be used in its licensed indication. All equipment being used within the UHL operating theatres for the purpose of the study will have approval/authorisation from the medical physics department. The data collected will be downloaded on to a tablet using Bluetooth technology. Cortisol measurements were initially obtained at baseline (for each surgeon), preoperatively /intraoperatively (at time of the removal of specimen) and postoperatively as a biomarker to measure the cognitive impact of surgery. However, process evaluation within the feasibility stage has revealed it to be inconvenient and a potential disruption to theatre workflow especially if more than one case is recruited per list. The cortisol measurements obtained thus far will be included in the preliminary analysis but this biomarker will be omitted in the data collected at the validation stage. Surgeons will be expected to complete the STAI and modified Nordic WMS questionnaires as well. The WMS questionnaires have been further modified following the process evaluation carried out throughout the feasibility stage – to now include a numerical pain score to further objectively evaluate the intensity of the work related injuries sustained/ experienced.

XSENS DOT

ACTIHEART HEART RATE MONITOR

The research involves working in collaboration with the wearable robotics team at Loughborough University.

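### The impact class is called objective although two of its four components are surgeon self-reports, and checking it against surgeon opinion does not give the planned subjective-versus-objective validation.

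*Protocol*

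**What the plan says.** **Label.** Protocol section 3 sets out to develop a tool "to objectively measure both the physical and psychological impact of complex surgical cases on a surgeon", giving one category per procedure. Section 3.3 repeats the claim. Section 2 looks ahead to a multi-centre study "which will provide objective evidence not only of patient outcomes but the impact of the different surgical routes on the surgeon".

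**Content.** Section 3.1 lists the components as "continuous HR monitoring; continuous movement sensor monitoring; STAI questionnaire; WMS questionnaire". Section 3.2, objective 1, is "Analysis to combine the 4 variables to give a single value of" impact, in three levels. On who answers the questionnaires, section 4 says "Surgeons will be expected to complete the STAI and modified Nordic WMS questionnaires as well". It adds that the WMS questionnaire was changed "to now include a numerical pain score to further objectively evaluate the intensity of the work related injuries".

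**Validation.** Section 3.2, objective 2, promises to validate the combined values by setting subjective against objective assessment. Section 10.3.2 compares the class with case complexity (BMI and previous surgery are the examples) and with the surgeon's subjective opinion.

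**Context.** Blinding is not applicable (section 7.4). The hypothesis in section 3 is that impact is lower with robotic surgery. Section 1 accepts that self-report matters when cognitive workload is measured.

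**The concern.** A measure that merges device readings with the operator's own answers is a mixed measure. Calling it objective claims more than its content supports, and a self-rated pain score does not become objective by being a number.

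The validation carries the more practical problem. If the class contains the surgeon's self-report and is then checked against the same surgeon's opinion, part of the agreement is one person's view compared with itself. The class takes the objective side of objective 2 although half its components are subjective. A tool could then go forward as validated with no evidence that its device measures agree with anything. Because the surgeon knows the route and the hypothesis has a direction, a route-related shift in the answers would also enter the class unseen unless the two parts are shown separately.

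**Working it through.** **1. Component count (sections 3.1 and 4).** Device: heart rate, movement. Self-report: STAI, WMS. Self-report share = 2/4 = 50%. Salivary cortisol, a laboratory measure, was dropped for the validation stage. With it the share was 2/5 = 40%. (Sections 3, 10.1 and 10.3.2 still speak of five points or components; the current list in 3.1 has four.) This is a count, not a weight: section 10.3.2 leaves the combination to statistical modelling.

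**2. Objective 2 beside its analysis.** Objective 2 needs a subjective measure and an objective one.

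| Comparison in 10.3.2 | One side | Other side |
|---|---|---|
| Class v. surgeon opinion | device + self-report | self-report |
| Class v. case complexity | device + self-report | patient features, e.g. BMI |

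Neither row sets a purely device-based quantity against a subjective one. The first row has self-report on both sides. I take the opinion to be that of the operating surgeon: section 11.1 attributes the complexity assessment to the patient's surgeon, and the section 7 schedule puts it after the operation among the surgeon's procedures. Section 7.6 refers more loosely to the patient's healthcare professional.

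**3. How shared self-report creates agreement.** Assumptions, none from the protocol: four equally weighted standardised components with mutual correlation r; surgeon opinion correlates q with each questionnaire and 0 with each device measure.

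- SD of the mean of the four = √((4 + 12r)/16) = 0.57, 0.69, 0.79 for r = 0.1, 0.3, 0.5.
- Correlation of the combined value with opinion = (0 + 0 + q + q)/4 ÷ SD = 0.5q/SD = 0.88q, 0.73q, 0.63q.
- These correlations can coexist if q²·[2 − 4r/(1+3r)]/(1 − r) < 1. The tightest case is r = 0.5: 2.4q² < 1, so q < 0.645.

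The combined value therefore keeps 63% to 88% of the questionnaires' own correlation with opinion, although the device measures have none. A separate comparison of opinion with the device sub-score would show 0.

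**4. How a reporting shift would carry into the class.** Same equal-weight model, cut at tertiles (±0.43 SD), no true route difference, both questionnaires reported b SD lower. Shift in the combined value δ = (2b/4)/SD. Share of cases dropping a class = Φ(−0.43+δ) − Φ(−0.43) + Φ(0.43+δ) − Φ(0.43).

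| b | r = 0 | r = 0.3 | r = 0.5 |
|---|---|---|---|
| 0.25 | δ 0.25, 18% | δ 0.18, 13% | δ 0.16, 11% |
| 0.5 | δ 0.50, 35% | δ 0.36, 26% | δ 0.32, 23% |

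These tables show the mechanism. They do not estimate a bias in this study, because b, q, r, the weights and the cut-points are all assumed.

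**The case against.** **Self-report is disclosed and justified.** Section 1 argues for it and section 3.1 names the questionnaires. This stands, and the point is not to remove them.

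**The parts are not lost.** Objectives 8 to 10 give heart rate, motion and the questionnaires their own data analysis, section 10.3.1 lists them separately, and section 10.5 asks whether every aspect of the tool is key to classification. A reader might infer that self-report can never be disentangled from the class, or that only the class will be reported. The protocol supports neither inference. What is absent is a requirement to use the separation in the validation.

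**The route comparison belongs to another study.** Section 10 plans none, section 3.3 assigns it to a later trial, and objective 5 leaves that trial's outcomes open. This stands. A reader might infer that preference for robotics will produce a false route difference, and attach an error rate to it. The protocol gives neither a reporting-bias size nor a number of cases per route; its 100 validation cases are the total, and surgeons contribute repeated procedures.

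**The equipoise remark is narrow.** Section 1 reports objections to a randomised trial in high-BMI patients, "including lack of equipoise amongst RA surgeons preventing them from randomising patients to SS". It concerns allocating patients and does not show that participating surgeons would under-report their own pain or anxiety.

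**Pre- and post-procedure questionnaires help.** Change scores could remove a surgeon's stable reporting level. They would not remove a route-specific shift in the post-operative answers.

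**Complexity is a second comparator.** BMI and previous surgery do not share the surgeon's self-report. They measure the case, however, and do not supply the subjective-versus-objective contrast.

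**Conclusion.** The point holds as one of labelling and validation. The combined class is a mixed device and self-report measure (2 of 4 components self-reported), so describing it, or the pain score, as objective is not supported by its content. Comparing it with surgeon opinion does not answer objective 2, since agreement can arise from self-report alone. This rests on the component list in 3.1 and on reading the opinion in 10.3.2 as the operating surgeon's.

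The primary outcome in 3.4 does not depend on any of this. The size of any route-related reporting bias is unknown and cannot be derived from the protocol. The consequence is a limit on what the tool can be said to show, and an objective that the planned comparison leaves unanswered.

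**What to change.** 1. In section 3.2 (objectives 1 and 2) and section 10.3.2, derive for each procedure a device sub-score (heart rate and motion) and a self-report sub-score (STAI and WMS) beside the combined class. Report all three in the validation.
2. In 10.3.2, compare surgeon opinion with the device sub-score separately, so that objective 2 has a subjective and an objective side.
3. In sections 2, 3, 3.3 and 4, describe the combined class as a mixed device and self-report measure, keep the word objective for the device measures, and stop applying it to the pain score.
4. State the limit of the device sub-score: it is not neutral between routes. Section 1 says straight-stick laparoscopy loads the shoulder and arm more, while robotic strain comes typically from the fixed console position. Upper-arm sensors (section 2) may miss the latter, which could favour the hypothesis.

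Cost: two derived values per procedure from data already collected, plus wording changes. The headline claim becomes weaker.

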3.1 Primary objective

The proportion of surgical procedures where all 4 variables of the assessment tool are captured (continuous HR monitoring; continuous movement sensor monitoring; STAI questionnaire; WMS questionnaire).

3.2 Secondary objectives

- 1. Analysis to combine the 4 variables to give a single value of 'impact' (high/intermediate/low) per procedure
- 2. Validation of the combined impact values (subjective vs objective assessment)
- To analyse the impact of providing surgical training and supervision to surgical traineeswith varying levels of experience within a live surgical setting using heart rate monitoring as objective measures (if the case has been deemed suitable by the Consultant for the trainee)
- 4. Willingness of recruitment of patients/surgeons and sample size calculations for a future multi-centre study
- 5. Identification of primary/secondary outcomes for a future definitive multi-centre study

- 6. Optimisation/validation of patient data recording measures to capture anaesthetic/operative/clinical events and outcomes
- 7. Safety assessment of measurement tools and recording devices in the theatre environment
- 8. Optimisation of surgeon continuous heart rate monitoring during procedure, data collection and analysis
- 9. Optimisation of positioning and recording of muscle movement/activity sensors and streamlining of data-analysis
- 10. Optimisation/validation of WMS and State Trait Anxiety Inventory (STAI) questionnaires and data analysis
- 11. To include the analysis of the cortisol samples collected at the feasibility stage within the preliminary analysis

